#### 9.6 Evaluation of Non-Target Lesions

Complete Response (CR)	Disappearance of all non-target lesions and normalization of tumor marker level. All lymph nodes must be non-pathological in size (<10 mm short axis)  Note: If tumor markers are initially above the upper normal limit, they must normalize for a subject to be considered in complete clinical response.
Non-CR/ Non-PD	Persistence of one or more non-target lesion(s) and/or maintenance of tumor marker level above the normal limits
Progressive Disease (PD)	Appearance of one or more new lesions and/or unequivocal progression of existing non-target lesions. Unequivocal progression should not normally trump target lesion status. It must be representative of overall disease status change, not a single lesion increase.

Although a clear progression of “non-target” lesions only is exceptional, the opinion of the site investigator should prevail in such circumstances, and the progression status should be confirmed at a later time by the sponsor investigator.

## 9.7 Evaluation of Best Overall Response

Target Lesions	Non-Target Lesions	New Lesions	Overall Response
CR	CR	No	CR
CR	Non-CR/ Non-PD	No	PR
CR	Not evaluated	No	PR
PR	Non-PD/ or not all evaluated	No	PR
SD	Non-PD or not all evaluated	No	SD
Not all evaluated	Non-PD	No	Non-evaluable
PD	Any	Yes or No	PD
Any	PD*	Yes or No	PD
Any	Any	Yes	PD

\*In exceptional circumstances, unequivocal progression in non-target lesions may be accepted as disease progression.

Subjects with a global deterioration of health status requiring discontinuation of treatment without objective evidence of disease progression at that time should be classified as having “symptomatic deterioration.” Every effort should be made to document the objective progression even after discontinuation of treatment.

## 9.8 Definitions for Response and Survival Evaluation

### 9.8.1 Time to Response (TTR)

The time between initiation of therapy and first documentation of PR or CR.

### 9.8.2 Radiologic Progression Free Survival (rPFS)

rPFS has two components to its definition. For soft tissue lesions, rPFS will be measured from Cycle 1 Day 1 to date of radiologic progression per RECIST 1.1 or death from any cause, whichever occurs first. For bone lesions (non-measurable disease), rPFS will be measured from Cycle 1 Day 1 to date of progression per PCWG3 criteria [9] or death from any cause, whichever occurs first. Thus, the “date of progression” is the earlier date of either of those two possible types of progression. Subjects who have not progressed will be right-censored at the date of the last disease evaluation.

### 9.8.3 Overall survival

Overall survival (OS) will be measured from Cycle 1 Day 1 to date of death from any cause. Patients still alive will be right-censored as of the most recent date on which they were last confirmed (by any of the methods listed) to be alive.

#### **9.8.4 Duration of Response (DoR)**

DoR will be measured from the start date of the best response achieved until the date of relapse (i.e., progression). Continuing responders will be right-censored as of the most recent date on which their response status had been assessed. DoR applies to only the patients who achieve either a complete response (CR) or a partial response (PR).

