#### 2.2.2 Secondary Endpoints

- Safety of the combination will be assessed based on Common Terminology Criteria for Adverse Events (CTCAE) version 5.0.
- Overall survival (OS) will be measured from date of registration to date of death from any cause.
- ORR will be the proportion of patients achieving either a complete response or a partial response, among all patients meeting the criteria of Section 12.6, as well as among all patients enrolled.
- DOR will be measured from the start date of the best response achieved until the date of relapse (i.e., progression).

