4: Chromogranin A, neuron specific enolase and urine NTx (optional) will be performed at screening/day 1 then prior to treatment every other Cycle starting at Cycle 3 Day 1 then at the D30 safety visit. PSA should be obtained at screening then prior to treatment every Cycle then at the D30 safety visit. Subjects that come off study without progression should have PSA obtained per investigator discretion. Testosterone will be performed at screening and at the D30 safety visit.

5: Tumor response assessment will consist of evaluation by CT scans of chest and MRI or CT of abdomen and pelvis. If a PET/CT is done for tumor assessment and if tumor/s are visible on the CT, this may be used for tumor evaluation. A bone scan will be obtained at screening and with other radiology imaging at the frequency as outlined below. An MRI of the brain should be performed at screening if there is a concern for the presence of brain metastases. Tumor imaging will be done at screening and every 3 cycles (9 weeks) for the first 12 cycles (36 weeks) and then every 4 cycles (12 weeks) until the patient is off study therapy (window of  $\pm$  1 week). Tumor imaging should follow week intervals in the case of study treatment delays due to toxicities. During follow up after completion of study treatment, imaging frequency is at the discretion of the site investigator. Imaging selected for each subject should remain the same throughout the study. Tumor imaging to be done at treatment discontinuation/safety follow up visit is at discretion of site investigator. If tumor assessments are available for subjects who have not yet experienced progressive disease (PD) at the time treatment is discontinued, the follow-up tumor evaluations will be documented in the eCRF until PD or death is confirmed, or until another treatment is initiated.

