### 12.4.2 Secondary Objective

For the first Secondary objective (safety assessment), the analysis of toxicity rates will be performed using only the toxicity-evaluable (t-e) patients. All patients receiving at least one dose of study medication will be t-e.

The grade of each type of toxicity (an ordinal categorical variable) will be summarized with 1-way frequency distributions. Dichotomized versions (e.g., the occurrence rate of Grade 3-4 fatigue) will be summarized as described in Section 12.4.1 for a binary endpoint.

For the second Secondary objective (follow up for survival), OS will be analyzed in the same fashion as rPFS. See Section 12.4.1.

For the third Secondary objective (ORR assessment), ORR will be analyzed in the same fashion as 6-month rPFS rate. See Section 12.4.1, first paragraph.

For the fourth Secondary objective (DoR assessment), DoR will be analyzed in the same fashion as rPFS. See Section 12.4.1, second paragraph.

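### Duration of response starts at best response and ends only at progression, so a deepening response loses time and a death in response is never an event

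*Combined protocol and SAP*

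**What the plan says.** Section 9.8.4 defines duration of response (DoR): "DoR will be measured from the start date of the best response achieved until the date of relapse (i.e., progression". Section 2.2.2 says the same, "DOR will be measured from the start date of the best response achieved until the date of relapse (i.e., progression", and section 12.2.2 repeats it and refers to 9.8.4 for further definition and censoring. The only censoring rule is in 9.8.4: "Continuing responders will be right-censored as of the most recent date on which their response status had been assessed". DoR covers CR and PR patients only. Death is not mentioned in any of the three places.

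Two neighbouring definitions differ. In section 9.8.2 the rPFS event is "radiologic progression per RECIST 1.1 or death from any cause, whichever occurs first". In section 9.8.1 time to response ends at the first documented PR or CR, not at the best response.

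For analysis, section 12.4.2 says "DoR will be analyzed in the same fashion as rPFS" and refers to the second paragraph of 12.4.1. That paragraph describes Kaplan-Meier estimation and defines no event.

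**The concern.** **Start date.** When a PR later becomes a CR, the time already spent in PR is discarded. Of two patients with the same first-response and progression dates, the one with the better response is given the shorter duration.

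**End date.** Progression is the only event. A responder who dies without documented progression does not count as one; the natural reading of 9.8.4 is that he is censored as a continuing responder at his last assessment. Kaplan-Meier then gives him the same later prospects as responders still alive, which lengthens the estimate.

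The protocol leaves room for such deaths. Calendar footnote 5 says "During follow up after completion of study treatment, imaging frequency is at the discretion of the site investigator", and section 6.7 leaves imaging to the site after treatment stops for reasons other than progression. Section 9.7 foresees treatment stopped for global deterioration without objective progression.

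At stake is the meaning of one reported secondary result and its consistency with rPFS. No decision rule uses DoR.

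**Working it through.** The plan states no DoR figure (no assumed median, event count or power), so there is none to reproduce.

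**1. Start date: arithmetic on the protocol's schedule**

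Calendar footnote 5: "Tumor imaging will be done at screening and every 3 cycles (9 weeks) for the first 12 cycles (36 weeks", then every 12 weeks. The scans fall at weeks 9, 18, 27, 36 and 48. Take PR at week 9 and progression at week 48:

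| CR first seen | DoR as written | DoR from first response | Lost |
|---|---|---|---|
| never (stays PR) | 48 − 9 = 39 | 39 | 0 |
| week 18 | 48 − 18 = 30 | 39 | 9 |
| week 27 | 48 − 27 = 21 | 39 | 18 |

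For a responder who progresses, time to response plus DoR should equal rPFS. In the second row the written rule gives 9 + 30 = 39 weeks against an rPFS of 48.

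**2. Death not an event**

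The documents do not give the share q of response endings that are deaths without progression; q = 10 to 30% is assumed. With constant hazards, censoring those deaths leaves a fraction (1 − q) of the event hazard, so the median is multiplied by 1/(1 − q): 1.11, 1.25 and 1.43 for q = 0.1, 0.2 and 0.3.

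With 7 responders (7/40 = 17.5%, assumed), the chance of at least one such death is 1 − (1 − q)^7 = 52%, 79% and 92%.

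**3. Both features together, large sample**

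Assumptions: exponential times with a true median of 39 weeks from first response to progression or death; 20% of responders deepen one scan (9 weeks) later if still in response; deaths are censored at the last 9-weekly scan.

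With no deaths this can be done by hand. The share still in response at 9 weeks is 2^(−9/39) = 0.852. Beyond 9 weeks the as-written curve is (0.8 + 0.2 × 0.852) × 2^(−t/39) = 0.970 × 2^(−t/39). Its median is 39 × log2(0.970/0.5) = 37.3 weeks.

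Simulation of 200,000 responders gives these as-written medians, in weeks:

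| Deepening | q = 0 | q = 0.1 | q = 0.2 | q = 0.3 |
|---|---|---|---|---|
| 20% | 37.3 | 41.4 | 46.5 | 52.8 |
| 40% | 35.7 | 39.5 | 44.6 | 51.3 |

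**4. Both features together, trial-sized sample**

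Same model with 20% deepening, 20,000 trials per setting, both definitions applied to the same patients. The entries are the share of trials in which the two medians differ by 9 weeks or more:

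| Responders | q = 0 | q = 0.1 | q = 0.2 |
|---|---|---|---|
| 7 | 11.5% | 22.8% | 34.0% |
| 10 | 9.2% | 25.9% | 42.8% |

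With 7 responders, the as-written median is the longer by that margin in 14.0% of trials and the shorter in 8.8% at q = 0.1; at q = 0.2 the figures are 27.1% and 6.9%. Sampling error alone puts 95% of correctly defined medians between about 11 and 95 weeks.

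**5. Milder assumptions**

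With 7 responders, 5% deepening and q = 5%, the medians differ by 9 weeks or more in about 9%, 7% and 4% of trials for true medians of 39, 26 and 17 weeks. They are identical in over 80%.

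**The case against.** **The text does not say that a death is censored.** True: it names progression as the only end, censors continuing responders, and gives no rule for a responder who dies. Section 12.4.2 likens the DoR analysis to rPFS, so an analyst might count deaths. But that reference leads only to the estimation paragraph, while 12.2.2 sends definition and censoring to 9.8.4, where death is absent. If both readings are possible, two analysts could report different results from the same data, which is itself a reason to fix the text. The start date is unaffected by this argument.

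**Duration of the best response is a legitimate quantity.** The wording is deliberate enough to appear three times, and it matters only for PR-to-CR conversion, which sections 9.5 and 9.6 make demanding. So few patients may be affected. The ordering it produces, with the deeper response scored shorter, remains hard to defend under the name duration of response.

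**The sizes rest on assumptions.** This stands for everything except the scan arithmetic. No document supports a particular death share, deepening share or median. Section 9.7 also asks sites to try to document progression after treatment stops, which should keep q down. Step 5 shows how small the effect becomes at the low end.

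**The endpoint is descriptive and imprecise.** Also true, and it limits how much this matters. Imprecision is not a reason to estimate the wrong quantity when the correction is a sentence.

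**Conclusion.** The definition is wrong as written on both counts. The start-date loss is certain for any PR that becomes a CR, at 9 or 18 weeks out of 39 in the examples. The omission of death follows from the literal text. If such deaths are censored, the median rises by a factor of 1.11 to 1.43 for an assumed death share of 10 to 30% under exponential times.

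The net direction is not known in advance. Under a 39-week true median and 20% deepening, the large-sample median runs from about 37 weeks with no such deaths to about 53 weeks at a 30% share. With 7 responders either shift is small against sampling error.

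DoR is a named secondary objective, so the wording should be corrected. The primary endpoint, the Simon boundaries and the sample size do not depend on it.

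**What to change.** In sections 2.2.2, 9.8.4 and 12.2.2, define DoR as the time from the first documented CR or PR to progression (dated as in 9.8.2) or death from any cause, whichever comes first. Right-censor responders who are alive and progression-free at their last disease assessment. Keep the Kaplan-Meier method of 12.4.1.

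The cost is one sentence in each section. The dates needed are those already required for time to response, rPFS and overall survival; the calendar includes survival status, and footnote 5 says "the follow-up tumor evaluations will be documented in the eCRF until PD or death is confirmed".

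Two limits should be acknowledged. That footnote applies where assessments are available and also stops at the start of another treatment, so some progressions may go undocumented. A death long after the last scan would then enter on the death date and could lengthen that patient's DoR. The rPFS definition in 9.8.2 already has this feature, and any rule for patients who start another therapy should be the same for both endpoints.

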### **10. DRUG INFORMATION**

#### **10.1 Pembrolizumab**

Pembrolizumab is a potent humanized immunoglobulin G4 (IgG4) monoclonal antibody (mAb) with high specificity of binding to the programmed cell death 1 (PD-1) receptor, thus inhibiting its interaction with programmed cell death ligand 1 (PD-L1) and programmed cell death ligand 2 (PD-L2). Based on preclinical in vitro data, pembrolizumab has high affinity and potent receptor blocking activity for PD-1. Pembrolizumab has an acceptable preclinical safety profile and is in clinical development as an intravenous (IV) immunotherapy for advanced malignancies.

Keytruda® (pembrolizumab) is indicated for the treatment of patients across a number of indications because of its mechanism of action to bind the PD-1 receptor on the T cell. For more details on specific indications refer to the Investigator brochure.

##### **10.1.1 Supplier/How Supplied**

Merck will supply pembrolizumab from commercial stock at no charge to subjects participating in this clinical trial.

The investigator at each site shall take responsibility for and shall take all steps to maintain appropriate records and ensure appropriate supply, storage, handling, distribution, and usage of investigational product in accordance with the protocol and any applicable laws and regulations.

##### **10.1.1 Preparation**

The product after reconstitution with sterile water for injection and the liquid drug product is a clear to opalescent solution, which may contain extraneous and proteinaceous particulates. The reconstituted product and liquid product is intended for IV administration. The reconstituted drug product solution and liquid drug product can be further diluted with normal saline in IV containers made of polyvinyl chloride (PVC) or non-PVC material. Reconstituted vials should be immediately used to prepare the infusion solution in the IV bag and the infusion solution should be immediately administered. If not used immediately, vials and/or IV bags may be stored at 2-8 °C for up to a cumulative time of 24 hours from time of dilution. If refrigerated, the vials and/or IV bags should be allowed to equilibrate to room temperature prior to subsequent use.

Pembrolizumab solutions may be stored at room temperature for a cumulative time of up to 6 hours. This includes room temperature storage of reconstituted drug product solution and liquid drug product in vials, room temperature storage of infusion solution in the IV bag and the duration of infusion. Please refer to the investigator's brochure for additional information.

##### **10.1.2 Storage and Stability**

Clinical supplies must be stored in a secure, limited-access location. Store vials under refrigeration at 2°C to 8°C (36°F to 46°F) in original carton to protect from light. Do not freeze. Do not shake. Receipt and dispensing of trial medication must be recorded by an authorized

person at the trial site. Clinical supplies may not be used for any purpose other than that stated in the protocol.

#### **10.1.3 Handling and Disposal**

Preparation should be performed by trained personnel in accordance with good practices rules, especially with respect to asepsis.

After final drug reconciliation, unused pembrolizumab vials should be disposed at the site following procedures for the disposal of anticancer drugs.

#### **10.1.4 Dispensing**

Pembrolizumab must be dispensed only from official study sites and to eligible subjects under the supervision of the site investigator. Pembrolizumab should be stored in a secure area according to local regulations. It is the responsibility of the site investigator to ensure that study drug is only dispensed to subjects.

#### **10.1.5 Adverse Events Associated with Pembrolizumab**

Pembrolizumab is generally well tolerated and demonstrates a favorable safety profile in comparison to chemotherapy. Pembrolizumab is an immunomodulatory agent, and based on this mechanism of action, immune mediated adverse events are of primary concern. Important identified risks for pembrolizumab are of an immune mediate nature, including: pneumonitis, colitis, hepatitis, nephritis, endocrinopathies that include hypophysitis (including hypopituitarism and secondary adrenal insufficiency), thyroid disorder (hypothyroidism, hyperthyroidism, thyroiditis), Type I diabetes mellitis, uveitis, myositis, Guillain-Barré syndrome, pancreatitis, myocarditis, myasthenic syndrome, encephalitis, sarcoidosis, severe skin reactions including Stevens-Johnson syndrome (SJS) and toxic epidermal necrolysis (TEN), some with fatal outcome; and “solid organ transplant rejection following pembrolizumab treatment in donor organ recipients” (risk applicable primarily to post-marketing setting only, as such patients are currently excluded from Merck-sponsored clinical studies with pembrolizumab).

The majority of immune-mediated adverse events were mild to moderate in severity, were manageable with appropriate care, and rarely required discontinuation of therapy.

Further details regarding immune-related adverse events (irAEs) can be found in the current version of the Investigator’s Brochure.

### **10.2 Lenvatinib**

Lenvatinib (lenvatinib mesilate) is an oral, potent multiple receptor tyrosine kinase (RTK) inhibitor that selectively inhibits vascular endothelial growth factor (VEGF) receptors, VEGFR1 (FLT1), VEGFR2 (KDR), and VEGFR3 (FLT4), in addition to other pro-angiogenic and oncogenic pathway-related RTKs including fibroblast growth factor (FGF) receptor FGFR1-4, platelet-derived growth factor (PDGF) receptor PDGFR $\alpha$ , KIT, and RET. Nonclinical studies showed lenvatinib to be a potent antiangiogenesis agent with antitumor activity versus various human cancer xenograft models in athymic mice.

### **10.2.1 Supplier/How Supplied**

Lenvatinib may be supplied in a 8 mg, 10 mg, 14 mg or 20 mg capsule. Lenvatinib drug substance is a white to pale yellow powder that is being used in the capsule formulation for the clinical studies evaluating lenvatinib. It is slightly soluble in water and has a molecular weight of 522.96 and a pKa of 5.27 (mesilate salt).

Merck will supply lenvatinib from clinical lots at no charge to subjects participating in this clinical trial.

The investigator at each site shall take responsibility for and shall take all steps to maintain appropriate records and ensure appropriate supply, storage, handling, distribution, and usage of investigational product in accordance with the protocol and any applicable laws and regulations.

### **10.1.2 Storage and Stability**

Lenvatinib capsules are packaged in cold form blisters or high-density polyethylene (HDPE) bottles with a polypropylene cap and desiccant. The blisters and bottles should be stored under room temperature.

### **10.1.3 Handling and Disposal**

Any unused medicinal product or waste material should be disposed of in accordance with local requirements. Do not open the capsule. Avoid repeat exposure to contents of the capsule.

### **10.1.4 Dispensing**

Lenvatinib must be dispensed only from official study sites and to eligible subjects under the supervision of the site investigator. Lenvatinib should be stored in a secure area according to local regulations. It is the responsibility of the site investigator to ensure that study drug is only dispensed to subjects.

### **10.1.5 Adverse Events Associated with Lenvatinib**

The most common adverse reactions include fatigue, arthralgia/myalgia, vomiting, nausea, stomatitis/oral inflammation, hypertension, headache, decreased appetite, stomach pain, hoarseness and rash, redness, itching or peeling of your skin on your hands and feet.

Further details around frequency, reporting, and management of adverse events (AEs) can be found in the current version of the Investigator's Brochure.

## 11. ADVERSE EVENTS

The descriptions and grading scales found in the NCI CTCAE v5 will be utilized for AE assessment. A copy of the CTCAE v5 can be downloaded from the CTEP website at <http://ctep.cancer.gov>. All forms for AE/SAE recording and reporting can be found in the EDC system (Documents and Information Tab).

### 11.1 Definitions

#### 11.1.1 Adverse Event (AE)

An AE is any untoward medical occurrence whether or not considered related to the study drug that appears to change in intensity during the course of the study. The following are examples of AEs:

- Unintended or unfavorable sign or symptom
- A disease temporally associated with participation in the protocol
- An intercurrent illness or injury that impairs the well-being of the subject

Hospitalization for elective surgery or routine clinical procedures that are not the result of an AE (e.g., surgical insertion of central line) should not be recorded as an AE.

Disease progression should not be recorded as an AE, unless it is attributable to the study regimen by the site investigator.

